STUDY PROTOCOL

PROTOCOL TITLE: A multi-centre randomised controlled trial of standard care versus an accelerated care pathway after cardiac surgery (FARSTER-care).

PROTOCOL SHORT TITLE: FARSTER-care

VERSION: 2.0

DATE: 22.10.2024

IRAS Number: 334434

ISRCTN Number: ISRCTN12204742

CORRESPONDING CHIEF INVESTIGATOR:

[name] [name], Honorary Professor at Hull York Medical School, Hull University; Consultant Cardiac Surgeon at Hull University Teaching Hospitals NHS Trust

COLLABORATORS:

[name], Lead Cardiac Rehabilitation Physiotherapist, Hull University Teaching Hospitals NHS Trust

[name], Reader, Department of Health Sciences, University of York

Miss [name], Senior Trial Statistician, Department of Health Sciences, University of York

[name], Consultant, South Tees Hospitals NHS Foundation Trust; Chair of Cardiac Surgery, Newcastle University

[name], Research Fellow, Department of Health Sciences, University of York

[name], Statistician, Department of Health Sciences, University of York

[name], Chair in Cardiovascular Health, Department of Health Sciences, University of York

[name], Senior Research Fellow, Centre for Health Economics, University of York

[name], PPI co-applicant

[name], PPI co-applicant

GENERAL INFORMATION:							
Study sponsor contact: [name], Hull University Teaching Hospitals NHS Trust							
Authorised by:							
Name: [name]	Role: Chief Investigator						
Signature:	Date:						
Name: [name]	Role: Sponsor Representative						

Date:

Signature:

STUDY SUMMARY

TITLE	A multi-centre randomised controlled trial of standard care versus an accelerated care pathway after cardiac surgery (FARSTER-care).			
ACRONYM	FARSTER-care			
Protocol Version	Version 2.0			
Date	23/09/2024			
IRAS	334434			
ISRCTN	12204742			
FUNDER	NIHR Health Technology Assessment Programme: NIHR152069			
Methodology	Multi-centre, two arm, parallel group, open RCT, including a health economic analysis.			
Study Duration	48 months			
Study Centres	At least 16 hospital sites across the United Kingdom.			
Objective	To determine whether, following cardiac surgery with sternotomy, early specialist outpatient review carried out at three weeks after hospital discharge followed by commencement of cardiac rehabilitation from four weeks will lead to improved patient outcomes and is cost effective compared to standard care, where outpatient review is typically six weeks after hospital discharge followed by commencement of cardiac rehabilitation from eight weeks.			
Number of Subjects/Patients	Using a 1:1 randomisation ratio, 588 patients will be randomised, stratified by centre, to intervention arm or a control (standard care) arm.			
Main Inclusion Criteria	Adults aged ≥18 years undergoing elective and urgent cardiac surgery who are having a full median sternotomy.			
Statistical Methodology and Analysis	For the analysis of the full trial (assuming continuation), participant flow will be presented using a CONSORT diagram. Analyses will be conducted on an intention-to-treat basis unless otherwise stated. Baseline and outcome data will be summarised by group and overall. Incremental Shuttle Walk Test (ISWT) distance will be analysed via mixed-effects repeated-measures linear regression, including sites and participant as random effects. Randomised treatment group and clinically important participant-level covariates including gender, age and Body Mass Index (BMI) will be included as fixed-effects. The secondary outcomes will be analysed using appropriate regression techniques based on the type of data controlling for the same covariates as included in the analysis of the primary outcome. Complier Average Casual Effect (CACE) analysis using two-stage least-squares instrumental variable regression will be carried out to assess the treatment effect in participants whose actual timing of Cardiac Rehabilitation (CR) commencing complied with the timing which			

was allocated. Remote patient review and home-based CR are now common practice but the impact of these on clinical outcomes, Patient Reported Outcome Measures (PROMs) and Quality of Life (QoL) are unknown. Baseline and outcome data will be summarised descriptively by group, stratified by whether patients received face-to-face or remote review, and home or centre-based CR.

Full analyses will be detailed in the trial's Statistical Analysis Plan (SAP), which will be reviewed and approved by the trial steering and data monitoring committees and finalised prior to the end of data collection.

PROTOCOL VERSION HISTORY LOG

Version	Date	Editor(s)	Comments
0.1	26/06/2023	[name]	Set-up document and drafted
			protocol
0.2	01/09/2023	[name], [name]	Review comments
		[name]	
0.3	12/09/2023	YTU trial team	Review comments
0.4	27/09/2023	[name], [name]	Additional health economic and
		[name]	statistics section included
0.5	11/10/2023	YTU trial team	Review comments
1.0	12/10/2023	YTU trial team	Finalised document
1.1	26/02/2024	[name]	Patient incentive wording
2.0	23/09/2024	[name]	Addition of inclusion criteria
			around ISWT completion and
			updated previous inclusion
			criteria to include patients who
			will receive CR as part of clinical
			pathway. Other updates to
			reflect trial procedures including
			reconfirmation of consent,
			duration of CR, timing of
			NSAE/SAE reporting, protocol
			deviations relating to
			appointment timings, and
			completion of questionnaires.
			Updated home-based CR
			protocol. Updated data
			collection and storage at YTU,
			recruiting and CR sites.

ABBREVIATIONS

AE Adverse Event

CABG Coronary Artery Bypasses Grafting

CI Chief Investigator

CONSORT Consolidated Standards of Reporting Trials statement

CR Cardiac Rehabilitation

CRF Case Report form

DMC Data Monitoring Committee

EQ-5D-5L EuroQol 5 Dimensions 5 Levels

GAD-7 Generalized Anxiety Disorder Scale

GCP Good Clinical Practice

ISWT Incremental Shuttle Walk Test

NHS National Health Service

NIHR National Institute for Health Research

NSAE Non-Serious Adverse Event

HRA Health Research Authority

PAG Patient Advisory Group

PIS Patient Information Sheet

PROM-CR Patient Reported Outcome Measure - Cardiac Rehabilitation

PSS Personal Social Services

QoL Quality of Life

RCT Randomised Controlled Trial

REC Research Ethics Committee

RN Research Nurse

SAE Serious Adverse Event

SAP Statistical Analysis Plan

SP Sternal Precautions

TMG Trial Management Group

TSC Trial Steering Committee

YTU York Trials Unit

CONTENTS

STUDY SUMMARY	3
PROTOCOL VERSION HISTORY LOG	5
ABBREVIATIONS	6
1. BACKGROUND AND RATIONALE	9
1.1 First postoperative outpatient review	9
1.2 Outpatient exercise-based cardiac rehabilitation	9
2. AIM AND OBJECTIVES	11
2.1 Aim	11
2.2 Objectives	12
3. STUDY DESIGN	12
3.1 Internal Pilot Study	13
3.2 Outcomes	14
4. STUDY POPULATION	15
4.1 Target population	15
4.2 Study sites	16
5. PARTICIPANT RECRUITMENT	16
5.1 Identification and consent of potential participants	16

1. BACKGROUND AND RATIONALE

In the UK, cardiac surgery has steadily increased since 2010, with 36,166 surgeries being

performed in 2016 [1]. In a survey we conducted in May/June 2017, 35 of the 42 UK cardiac

centres responded, and confirmed this it is current practice that, following cardiac surgery,

patients attend their first outpatient review approximately six weeks after hospital discharge,

where recovery is assessed and fitness to commence Cardiac Rehabilitation (CR) is

determined; CR is then started from eight weeks [2].

The standard access for cardiac surgery is through a median sternotomy [3,4,5,6], following

which patients are required to refrain from upper body exercises, lifting of heavy objects and

usual strenuous activities for 12 weeks [7,8,9,10]. These restrictions, called "Sternal

Precautions" (SP), are intended to aid healing of the cut breastbone. CR, which has significant

short- and long-term benefits after cardiac surgery [11,12], is therefore delayed. Current time

frames for outpatient review and CR are not evidence-based and may prolong recovery after

cardiac surgery and be placing unnecessary limitations on patient activity.

1.1 First postoperative outpatient review

The long interval before outpatient review and CR extends the period of vulnerability and

inactivity for patients, with patients often seeking medical attention for surgery-related

complications during this period [13,14,15]. In a prospective observational study, we found

that 38.9% of patients reported surgery-related complications and sought further medical

help during this six-week period (15.3% required readmission), and 44.4% would like an

earlier review [2].

Early contact with patients has been associated with reduction in hospital readmissions [16].

Non-randomised studies have also shown lower 30-day adverse outcomes with early review,

for cardiac and other surgical patients [16, 17].

1.2 Outpatient exercise-based cardiac rehabilitation

In current UK best practice, cardiac surgery patients commence CR around eight weeks from

referral; however, 45% of programmes do not meet these standards with wait times over

FARSTER-care Protocol

V2.0 22.10.2024 IRAS reference: 334434 ISRCTN: 12204742 eleven weeks after hospital discharge [18]. Current guidelines for activity and exercise after median sternotomy have been described as restrictive, conflicting, sometimes arbitrary, frequently anecdotal, and occasionally based on expert opinion [8]. The delay in starting CR can mitigate the benefits of CR [19], contribute to physical deconditioning, and hinder the ability of CR to facilitate timely recovery of fitness and physical activity status [20]. LaPier et al reported functional limitation following sternotomy [21] and related this to surgeon-dictated SP [20]. Furthermore, the delay in starting CR can prolong the recovery process, increase dependence on family and/or carers and can cause frustration. This may contribute to anxiety and depression that is reported in patients recovering after Coronary Artery Bypass Graft (CABG) [22]. According to the 2013 UK national audit of CR, late CR commencement contributes to a substantial number of heart surgery patients declining to participate in CR [23].

Early initiation and progressive physical exercise after cardiac surgery have well known benefits [24, 25] and prolonged restrictions of physical activities appear detrimental to patient health and wellbeing. A small observational study noted that functional recovery to pre-surgery levels was achievable at two months with physical therapy [26]. A Randomised Control Trial (RCT) which compared the effectiveness and safety of CR from two weeks post sternotomy with that of standard care, concluded that with 'appropriate precautions' CR can be started from two weeks post-sternotomy, although this conclusion was made cautiously due to limitations within the trial [27, 28]. The timing of CR impacts functional recovery and level of physical fitness after cardiac surgery [29,30,31,32]. Improvement in post sternotomy symptoms [33] is also associated with physical activity. The British Associate for Cardiovascular Prevention and Rehabilitation (BACPR) standards and core components [34] and National Certification Programme (NCP) for CR [35] recommend early commencement of CR which is monitored by National Audit of Cardiac Rehabilitation (NACR) 2018 [18], showing that early rehabilitation is a performance standard for all programmes in patients following coronary artery stents or post-heart attack conservative pathways [18].

There are variations in types of exercises permitted, limits for weight of objects that can be lifted, guidelines for activities, and timeline for resumption of driving. Parker et al [36] demonstrated that the force elicited on the breastbone by coughing far exceeded lifting above the recommended limit. Adams and colleagues [8] investigated forces associated with

FARSTER-care Protocol
IRAS reference: 334434

32 activities of daily living and reported that the majority not restricted by SP, such as opening and closing doors, generated forces greater than the weight limit allowed. While SP may help to support bone healing, the optimal nature and duration are unclear especially since sternal bone healing occurs by five weeks [9]. Our observational study (FORCAST6) showed that the incidence of postoperative complications is highest in the first week after hospital discharge and declines to lowest levels by four weeks [2]. The logic for the timing of early CR is associated with this area of postoperative stability and will therefore commence at five weeks after surgery (four weeks after hospital discharge).

In summary, published data is lacking about the appropriate timing of postoperative review and CR following cardiac surgery. The dominant role of SP as a deterrent to early CR after cardiac surgery has been questioned [9,10]. Cahalin and associates [10] identified major setbacks with current SP practice to include: lack of supporting evidence, variation between institutions, lack of universally accepted definition, and the functional limitations they engender. A similar experience was reported in Europe [37] and Australia [38]. These inconsistencies create a dilemma for patients, their families, and healthcare professionals alike. Nevertheless, SP continues to inform conventional practice and recommendations of The British Heart Foundation (BHF) [7].

Our feasibility study established that bringing forward outpatient review and CR, in order to facilitate recovery, physical fitness and Quality of Life (QoL) was acceptable to patients and that a full scale RCT was feasible [39]. This RCT aims to provide robust evidence to underpin a post-cardiac surgery care pathway that facilitate fast, clinically efficient, and cost-effective recovery, with improved patient outcomes.

2. AIM AND OBJECTIVES

2.1 Aim

To determine whether, following cardiac surgery with sternotomy, early specialist outpatient review carried out at three weeks after hospital discharge followed by commencement of CR from four weeks, leads to improved outcomes and is cost effective compared to standard care, where the outpatient review is six weeks after hospital discharge followed by commencement of CR from eight weeks.

2.2 Objectives

To undertake a randomised parallel group comparison to determine the effects of

early CR on physical functional capacity using the using incremental shuttle walk test

(ISWT) at six months post-randomisation (primary outcome).

ii. To undertake an eight-month internal pilot to obtain robust estimates of recruitment

and retention ensuring trial viability.

iii. To undertake a randomised parallel group comparison to determine the effects of

early CR on outcomes related to physical health and psychological health at six- and

twelve-months post-randomisation.

iv. To conduct a detailed economic evaluation to assess the cost-effectiveness of early CR.

3. STUDY DESIGN

The study design has been informed by the results of a feasibility study (FARSTER) [39], which

demonstrated that it would be acceptable and feasible to undertake a full-scale trial, subject

to some modifications to maximise recruitment. The objectives of FARSTER-care will be

addressed using a multi-centre, two arm, parallel group, open RCT, including an internal pilot

study and embedded health economic analysis. The trial will recruit 588 cardiac surgery

participants who have had a sternotomy at UK centres over 24 months and will randomise

participants 1:1 to the FARSTER-care (intervention) or standard care (control) arms.

Participants in the intervention arm will have specialist outpatient review at three weeks after

hospital discharge, followed by commencement of CR from four weeks. Participants in the

standard care arm will receive standard post-sternotomy cardiac surgery care which includes

specialist outpatient review at six weeks after hospital discharge, followed by commencement

of CR from eight weeks.

At the start and end of CR, and again at six months post-randomisation, participants will

undergo fitness testing using the ISWT during face-to-face appointments. Clinical data will be

recorded at baseline and appointments up to six months post-randomisation. Participants will

be asked to self-report outcome data by completing questionnaires from baseline up to

FARSTER-care Protocol IRAS reference: 334434 V2.0 22.10.2024

twelve months post-randomisation. The study flow chart (Figure 1) and study assessment schedule (Figure 2) detail the study timelines.

3.1 Internal Pilot Study

The first eight months of recruitment will constitute an internal pilot phase, after which progress will be assessed against pre-specified criteria using a traffic light system (red/amber/green) (Table 1). The outcome of the pilot study will enable a confirmation of whether the trial is feasible and determine progression to the main trial. The criteria assessed relate to the recruitment of sites and participants, deliverability of the intervention, and rate of follow-up for the primary outcome. The recruitment rates and number of sites open are based on the projected recruitment targets for the 24-month recruitment period. Results will be compared against the study's recruitment assumptions and progression targets, and continuation of the trial or relevant modifications will be decided by the Trial Steering Committee (TSC) and the funding body.

Table 1. Internal pilot progression criteria.

	Red	Amber	Green
Recruitment rate/site/month	<1	1-1.9	≥2
Number of sites opened	<5	5-7	≥8
Collection of ISWT at the post-CR timepoint	<60%	60-84%	≥85%
Adherence with intervention pathway (difference between average	<2	2-3	3+
time between surgery and CR between the two groups in weeks)			

The actions taken for the progression criteria are outlined below:

- Green: continue the trial.
- Amber: review procedures to identify underlying problems, and put in place strategies
 to address these, review after an interval and if recruitment trajectory does not
 indicate that full recruitment will occur within scheduled recruitment period, discuss
 next steps with TSC and funder.
- Red: terminate the trial unless we can confidently identify successful strategies or rapidly resolve the problem.

FARSTER-care Protocol IRAS reference: 334434

V2.0_22.10.2024 ISRCTN: 12204742 3.2 Outcomes

Primary outcome

The primary outcome is the difference in ISWT (meters walked) between the treatment

groups at six months post-randomisation. The ISWT is a functional capacity test used to

measure physical fitness and is widely used in CR programmes in the UK [40]. Participants will

be asked to perform this test before their CR commences (pre-CR time point), once CR

finishes (post-CR time point) and at the six-month time point.

Secondary outcomes

Secondary outcomes will be collected at baseline, pre-CR, post-CR, six- and twelve- months

post-randomisation (see Figure 2: Study assessment schedule). The secondary outcomes

include:

Physical health

• **Heart rate**: Measured in beats per minute using a pulse oximeter.

o **Blood pressure**: Systolic and diastolic blood pressure measured following

standard site procedure and recorded in mmHg.

Oxygen saturation: Measured using a pulse oximeter showing the percentage

of oxygen in the blood.

Patient outcomes

o Patient Reported Outcome Measure - Cardiac Rehabilitation (PROM-CR): A

patient-reported questionnaire designed and validated for cardiac

rehabilitation which asks a patient how much their heart condition has

impacted their life over the preceding two weeks in relation to physical, social

and lifestyle, emotional and care aspects [41].

Psychological health

o **Generalized Anxiety Disorder Scale (GAD-7**): The GAD-7 is a seven-item self-

administered patient questionnaire used as a screening tool and severity

measure for generalised anxiety disorder [42].

Quality of life

- EQ-5D-5L: The EQ-5D-5L is a validated generic patient-reported outcome measure [43, 44]. The descriptive system has five health domains (mobility, self-care, usual activities, pain/discomfort, and anxiety/depression) with five response options for each domain (no problems, slight problems, moderate problems, severe problems, and extreme problems). In addition, it has a health status Visual Analogue Scale (VAS) which measures self-rated health with endpoints ranging from 'the best health you can imagine' to 'the worst health you can imagine'.
- National Health Service (NHS) resource use
 - NHS resource use questionnaire: Patient reported NHS and Personal Social
 Services (PSS) resource use will be collected using bespoke questionnaire.

Complications

- These will be collected in the documentation at baseline and six months, and throughout the trial in the form of adverse events.
- CR uptake
 - o This will be recorded in the CR session logs.

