5.2 Screening for eligibility

Following their surgery, patient eligibility will be confirmed by the clinical team. An *Eligibility Screening Checklist* will be completed and for those patients deemed ineligible, reasons for their ineligibility (including not willing to provide consent) will be recorded anonymously. Screening for complications that would render a patient ineligible can be done anytime during the hospital stay, before randomisation. Patients will be screened against the inclusion and exclusion criteria in Section 4.1.

FARSTER-care Protocol IRAS reference: 334434

V2.0_22.10.2024 ISRCTN: 12204742 6. BASELINE DATA COLLECTION

Prior to randomisation all consenting patients will undergo baseline assessment, including a

questionnaire and clinical assessments. The Participant Baseline Questionnaire will include

patient demographics, and questionnaires related to the secondary outcomes. An

appropriately trained member of the research team at the site will carry out baseline

assessments. Data will be recorded in the Clinician Baseline Form.

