9. INITIAL CARDIAC REHABILITATION APPOINTMENT (PRE-CR TIMEPOINT)

Participants referred for CR will be offered a comprehensive programme including an assessment carried out at their initial cardiac rehabilitation appointment, prior to starting their programme in line with the recruiting sites' policies. The initial appointment will take place as near as possible to four weeks post-hospital discharge in the FARSTER-care group and as near as possible to eight weeks post-hospital discharge in the standard care group.

This appointment will be a face-to-face appointment where the participant will perform the ISWT and will be provided with advice on cardiac risk factor reduction. This will typically include information on medication, diet, exercise, and physical activity as well as psychosocial wellbeing and smoking cessation. Participants will be offered further education sessions on

cardiac risk factor reduction during the programme. These would be delivered by specialist CR staff. Referral to other healthcare professionals such as specialist counsellors, pharmacists and dieticians may also be considered if necessary. Unless contraindicated, referral to the exercise component of the CR programme will be made. Following this initial assessment, participants will be enrolled in exercise programmes. Data from the initial CR appointment will be recorded in the *Clinician Pre-CR Form*. If a participant does not attend this appointment, they will be sent another appointment.

During this appointment, participants will be asked to complete PROM-CR, EQ-5D-5L, GAD-7 and resource use questions (*Participant Pre-rehabilitation [control or intervention] Questionnaire*). If required, the trial team at YTU may send this questionnaire to the participant, either electronically or by post.

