13. TWELVE MONTH FOLLOW UP

About twelve months (52 weeks) after randomisation, all study participants will be invited to complete EQ-5D-5L, GAD-7, and NHS resource use, costs, and time off work questions (*Participant 12-month Questionnaire*). The trial team at YTU will manage the follow-up at this timepoint. Participants can opt to complete the questionnaire electronically, by post or by telephone.

Figure 2: Study assessment schedule

	Baseline			Post-randomisation				
	Pre- surgery	Post- surgery	Outpt. review	Pre- CR	CR	Post -CR	6m FU	12m FU
Screening for eligibility		Χ						
Consent	X	Χ						
Baseline data collection		Χ						
Randomisation		Х						
Clinical assessment		X*	Χ*				Χ	
ISWT				X*		Χ*	Χ	
PROM-CR				Х		Х	Х	
EQ-5D-5L		Х		Х		Х	Χ	Х
GAD-7		Χ		Х		Х	Χ	Х
CR assessments				X*		Χ*		
Vital signs – heart rate, blood pressure, oxygen saturation		X*	X*	X*		X*	Х	
CR session logs					Х			
Resource use questions				Х			Χ	Х
Adverse event monitoring			X*	Х		Х	Х	Х

^{*}part of normal patient pathway

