18.2 Statistical and analytical plans

For the analysis of the full trial (assuming continuation from the internal pilot trial), participant flow will be presented using a CONSORT diagram. Analyses will be conducted on an intention-to-treat basis unless otherwise stated. Baseline and outcome data will be summarised by group and overall. The ISWT distance will be analysed via mixed-effects repeated-measures linear regression, including site and participant as random effects. Randomised treatment group and clinically important participant-level covariates including gender, age and BMI will be included as fixed effects. CACE analysis using two-stage least-squares instrumental variable regression will be carried out to assess the treatment effect in participants whose actual timing of CR commencing complied with the timing which was allocated.

The secondary outcomes will be analysed using appropriate regression techniques based on the type of data controlling for the same covariates as included in the analysis of the primary outcome, plus baseline value of the outcomes where available.

Remote patient review and home-based CR are now common practice but the impact of these on clinical outcomes, PROMs and QoL are unknown. Details on intervention delivery and adherence will be presented, and baseline and outcome data will be summarised descriptively by group, stratified by whether patients received face-to-face or remote review, and home or centre-based CR.

Full analyses will be detailed in the trial's statistical analysis plan (SAP), which will be reviewed and approved by the trial steering and data monitoring committees and finalised prior to the end of data collection.

FARSTER-care Protocol IRAS reference: 334434

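### Section 3.2 lists a baseline collection of PROM-CR that Figure 2 does not schedule, so this secondary outcome cannot gain precision from baseline adjustment

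*Protocol*

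**What the plan says.** Section 3.2 gives one collective sentence on timing: "Secondary outcomes will be collected at baseline, pre-CR, post-CR, six- and twelve- months", and it continues "post-randomisation (see Figure 2: Study assessment schedule". The list beneath it includes "Patient Reported Outcome Measure - Cardiac Rehabilitation (PROM-CR): A" questionnaire described as designed and validated for cardiac rehabilitation, with a two-week recall.

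Section 6 says that the Participant Baseline Questionnaire holds "patient demographics, and questionnaires related to the secondary outcomes", without naming any instrument.

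"Figure 2: Study assessment schedule" marks EQ-5D-5L and GAD-7 at the post-surgery baseline, pre-CR, post-CR, six months and twelve months. It marks PROM-CR only at pre-CR, post-CR and six months. The text agrees with the figure. Section 9 says that at the initial CR appointment "participants will be asked to complete PROM-CR, EQ-5D-5L, GAD-7"; sections 11 and 12 name PROM-CR at post-CR and six months; section 13 does not name it at twelve months.

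Section 18.2 analyses the secondary outcomes with the covariates of the primary analysis, "plus baseline value of the outcomes where available".

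**The concern.** Someone reading section 3.2 would expect a PROM-CR score before randomisation. A site working from Figure 2 will not collect one. The gap is permanent for each participant, because a pre-randomisation score cannot be obtained afterwards and no later analysis plan can supply it.

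At stake is the precision of the six-month PROM-CR comparison. Of the three patient-reported scales (PROM-CR, EQ-5D-5L, GAD-7), PROM-CR is the only one specific to cardiac rehabilitation and the only one without a baseline. Balance between the arms on PROM-CR at entry also cannot be described.

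**Working it through.** **Step 1: compare the passages on PROM-CR timing.**

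| Time point | Section 3.2 sentence | Figure 2 | Sections 9, 11, 12, 13 |
|---|---|---|---|
| Baseline (post-surgery) | yes | no | no mention (section 6 names no instrument) |
| Pre-CR | yes | yes | yes (section 9) |
| Post-CR | yes | yes | yes (section 11) |
| Six months | yes | yes | yes (section 12) |
| Twelve months | yes | no | no (section 13) |

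The sentence and the schedule disagree at two points, baseline and twelve months. The schedule and the visit sections agree throughout, so a broken table does not explain the difference. By schedule, PROM-CR has no measurement before randomisation and three after it.

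**Step 2: can the first scheduled value serve as a baseline?** No. It is taken after randomisation, at about four weeks after discharge in the intervention arm and "as near as possible to eight weeks post-hospital discharge in the standard care group". The arms are measured about 8 − 4 = 4 weeks apart in recovery.

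**Step 3: the number analysed.** Section 18.1 gives a standardised effect of 0.3, 90% power, 5% two-sided significance and 20% attrition. A two-sample t-test needs 235 per arm, 470 in total, and 470/0.8 = 587.5, rounded up to 588. The plan's figure is reproduced. I assume that the same 470 provide PROM-CR at six months; the protocol gives no separate figure.

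**Step 4: precision with and without a baseline.** In SD units and with 1:1 allocation, the unadjusted standard error of the difference is √(2/235) = 2/√470 = 0.092. Adjustment for a baseline with correlation r multiplies it by √(1 − r²). The equivalent unadjusted sample is 470/(1 − r²). The effect detectable with 90% power is (1.960 + 1.282) × SE. The protocol gives no correlation for PROM-CR, so the values of r are assumptions.

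| Assumed r | Variance factor 1 − r² | SE (SD) | Equivalent N | Detectable effect (SD) |
|---|---|---|---|---|
| 0 (no baseline) | 1.00 | 0.092 | 470 | 0.299 |
| 0.3 | 0.91 | 0.088 | 516 | 0.285 |
| 0.4 | 0.84 | 0.085 | 560 | 0.274 |
| 0.5 | 0.75 | 0.080 | 627 | 0.259 |

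The trial's sample size does not change, because it rests on the ISWT.

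**The case against.** The best defence is that the schedule is coherent and only one summary sentence is loose. That sentence points to Figure 2 for detail, and taken literally it fails for other outcomes too: resource use has no baseline mark and vital signs have none at twelve months. Omitting PROM-CR at baseline may also be deliberate. The recall period is two weeks, and section 1.2 equates five weeks after surgery with four weeks after discharge, so the stay is about one week. An in-hospital score would look back across the operation and the admission, and might correlate weakly with six months. Much of this stands: it limits the gain and suggests a drafting slip. It does not make section 3.2 correct, and it does not give PROM-CR a baseline.

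A reader might infer more than the protocol supports:

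- **That section 18.2 intends to baseline-adjust PROM-CR and is thwarted.** Its adjustment is conditional, so outcomes without a baseline are provided for.
- **That section 6 also contradicts Figure 2.** It names no instrument, and EQ-5D-5L and GAD-7 satisfy its wording. It is ambiguous.
- **That PROM-CR is the only questionnaire without a baseline.** The resource use questionnaire has none either.
- **That the comparison is biased.** Chance imbalance under randomisation is already reflected in the standard error. Bias could enter if the pre-CR score were used as a baseline covariate, but no section proposes that, so no bias figure belongs in the size of this point.
- **That dropout cannot be examined.** Baseline EQ-5D-5L, GAD-7, clinical and demographic data are available for that.

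**Conclusion.** The inconsistency is real: section 3.2 promises PROM-CR at baseline and twelve months, while Figure 2 and the visit sections collect it at neither. The statistical consequence is confined to precision on one secondary outcome. The unadjusted comparison remains valid. A baseline would lower its variance by 9% to 25% if the correlation with six months lies between 0.3 and 0.5. That range is assumed; a weaker correlation for an in-hospital score would give less. The size also assumes that PROM-CR completion at six months matches the 20% attrition planned for the primary outcome. This is a worthwhile, inexpensive improvement and a necessary wording correction. It does not threaten the primary result.

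**What to change.** 1. Add PROM-CR to the Participant Baseline Questionnaire and mark it in the post-surgery column of Figure 2.
2. In section 18.2, name the pre-randomisation PROM-CR score as the baseline covariate for that outcome.
3. Reword section 3.2 to give time points for each secondary outcome, including that PROM-CR is not collected at twelve months. Adding the baseline mark alone would leave that second mismatch in place.

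The cost is a few minutes per in-patient, on a form that already carries EQ-5D-5L and GAD-7, plus an amendment. People already enrolled gain nothing; how their missing baselines are handled is a matter for the analysis plan. The gain may be small because of the recall window.

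If the sponsor prefers not to add the measurement, the minimum is to correct section 3.2 to say that PROM-CR has no baseline, and to state that the pre-CR score is not used as a substitute.
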